Influence of Walnut (*Juglans regia*) Intake on Acute Adverse Effects Induced by High Saturated Fat Meals in Obese and Diabetic Women

20 August, 2024

RESEARCH PROJECT

**Influence of Walnut (*Juglans regia*) Intake on
Acute Adverse Effects Induced by High
Saturated Fat Meals in Obese and Diabetic
Women**

Researchers: [name]. [name]
[name]. [name]

Botucatu, São Paulo, Brazil
2024

Initial Considerations

The consumption of high-fat meals, particularly those rich in saturated fats, is increasing in Brazil and contributing to the rise of chronic non-communicable diseases, including obesity and diabetes. The known chronic effects of these diets arise from acute adverse effects, such as increased inflammation and oxidative stress, making it crucial to investigate the potential of certain foods to counteract the harmful effects of an unhealthy diet. In this context, chronic nut consumption is associated with reduced cardiovascular outcomes. Although some evidence also suggests benefits in the short term, studies of short duration are very limited. However, the mechanisms involved in the beneficial effects of nut intake remain to be elucidated. In our study, we aim to investigate whether circulating microRNA profiles and metabolomic profiles can contribute to pathways related to the beneficial effects of nut intake. These pathways are identified through bioinformatics analysis and may inform the mechanisms of action of nuts, as well as aid in obesity prevention and treatment. Additionally, bioinformatics analysis and pathway identification may contribute to developing diagnostic and prognostic algorithms in artificial intelligence.

This study employs advanced methodologies and may contribute to the treatment of obesity and type II diabetes, conditions affecting more than 20% of the Brazilian population. The clinical trial will be conducted at the Botucatu Medical School, and biological material will be collected for further analysis at Monash University, Australia. Both institutions have a strong research tradition and laboratory facilities to support the project. [name], the project coordinator, has expertise in nutrition and studies on acute supplementation of bioactive compounds. He is an Associate Professor in the Department of Clinical Medicine at Botucatu

Obesity is a multifactorial disease in which excess body fat accumulation increases the risk of other chronic diseases such as type 2 diabetes. The primary cause of obesity is the energy imbalance between calories consumed and expended. A balanced diet is essential for weight control and maintaining a healthy body weight. In this context, the consumption of high saturated fat meals (HSFM) plays a detrimental role, contributing to the development of obesity, type 2 diabetes, cancer, cardiovascular diseases, and exacerbating chronic inflammation. Additionally, it may induce metabolic endotoxemia and modulate circulating microRNA profiles. Thus, due to the harmful health impacts of HSFM, studies on metabolomics and circulating microRNA levels could enhance understanding of the mechanisms by which walnuts (*Juglans regia*) prevent and treat diseases.

The objective of this study is to evaluate whether acute walnut supplementation attenuates the inflammatory response, oxidative stress, glycemic response, and regulates the metabolomic and circulating microRNA responses induced by HSFM in women with obesity and type 2 diabetes. The study will be randomized and cross-over, including obese and non-insulin-dependent diabetic women over 18 years of age without other comorbidities. In the first session, participants will arrive at the clinic after a 10-hour fast and will be offered HSFM with or without 30g of walnuts. In the second session, those who did not receive walnuts will now receive them with HSFM, and vice versa. Blood samples will be collected, and serum insulin, glucose, inflammatory biomarkers, and oxidative stress will be assessed. TNF-alpha, IL-6, IL-1 β , IL-1ra, IL-8, and IL-10 will be measured by ELISA, and MDA by HPLC. Additionally, metabolomic and microRNA

analyses will be conducted. Data analysis will be performed using JAMOVI v 2.3.21, with a significance level of 5%.

Introduction

Obesity is a multifactorial disease in which excess body fat accumulation leads to negative health effects [1]. It is considered a global public health problem, mainly due to its association with an increased risk of developing other non-communicable chronic diseases (NCDs) [2]. According to the World Obesity Atlas 2023 report, 38% of the global population is currently overweight or obese. Additionally, it is projected that 78% of adults in the U.S. will be overweight/obese [1,3]. In Brazil, it is estimated that one-quarter of the population is obese, making this a significant risk factor for pathological aging [4].

The primary cause of obesity is the energy imbalance between calories consumed and expended, and its high prevalence is associated with physical inactivity and sedentary behavior [5]. A balanced diet, with the consumption of whole and minimally processed foods, is known to be essential for weight control. However, in the current scenario, there has been a significant increase in the consumption of ultra-processed foods and a reduction in the intake of whole and minimally processed foods, resulting in a substantial impact on the prevalence of obesity [6, 7].

Obesity is one of the most relevant risk factors for type 2 diabetes, a disease that is increasingly prevalent worldwide and is considered one of the health emergencies of the 21st century. Diabetes impacts morbidity and mortality and is also a major risk factor for stroke, renal dysfunction, cardiovascular diseases, vision loss, and neuropathy [8]. Non-pharmacological strategies for controlling diabetes typically include nutritional

intervention, regular physical activity, smoking cessation, and maintaining a healthy body weight [10, 11].

Acute intake of macronutrients can induce adverse responses even in healthy individuals [9–19], which can lead to chronic effects over time. In this context, the consumption of high saturated fat meals (HSFM) plays an important role, as chronic consumption of an HSFM diet is known to contribute to the development of obesity, type 2 diabetes, cancer, and cardiovascular diseases, in addition to exacerbating chronic inflammation induced by insulin resistance and excess weight [9]. Furthermore, studies show that an HSFM can also induce metabolic endotoxemia and modulate circulating microRNA profiles [20]. MicroRNAs are non-coding RNA molecules approximately 22 nucleotides in length that regulate gene expression at the post-transcriptional level by degrading mRNA or inhibiting the translation of target genes [21]. Thus, microRNAs may contribute to the adverse effects of an HSFM.

Given the detrimental health impacts of HSFM, studies have been conducted with acute supplementation of foods with anti-inflammatory and antioxidant properties, such as orange juice and green tea [17-22], in order to minimize the negative effects of an unhealthy diet. A study conducted by our research group showed that acute supplementation of green tea inhibited the expression of 62 microRNAs induced by HSFM intake [22]. Bioinformatics analysis indicated that these microRNAs regulated genes associated with TGF-beta, CARM1, RSK, and BMP pathways [22]. The identification of these miRNAs and their molecular pathways can contribute to understanding the benefits of dietary compounds for health and disease.

Regular walnut (*Juglans regia*) consumption is associated with better cardiovascular health [23] and insulin response, possibly due to the regulation of insulin response by reducing the activity of carbohydrate-digesting enzymes [24]. However, the

literature remains limited and inconclusive regarding the effects of walnuts on the inflammatory and antioxidant response [25]. Additionally, there is only a limited number of studies investigating the acute effects of walnuts, with indications of positive response. In this regard, postprandial attenuation of insulin resistance, improved endothelial function, oxidative stress, and satiety have been demonstrated in some but not all studies [26-29]. Interestingly, Torabian et al. [27], in an intervention study, observed that acute walnut consumption increased plasma concentrations of polyphenols, as well as enhancing total antioxidant capacity and reducing plasma lipid peroxidation.

In addition to the limited evidence regarding the acute effects of walnuts, their effects alongside HSFM on metabolomic and microRNA profiles have not yet been studied. Metabolomics was initially defined as the quantitative measurement of the dynamic multiparametric metabolic response of living systems to physiopathological stimuli or genetic modification. Thus, it directly reflects the phenotype of a particular biological system at the molecular metabolic level, also allowing for the detection of changes in previously unknown, uncharacterized, or rarely reported metabolites [29]. In this way, metabolomics can provide important insights into the mechanisms of walnuts in the prevention and treatment of diseases. The same applies to the study of microRNAs, which can aid in identifying the intracellular pathways related to the beneficial effects of walnut consumption.

Therefore, this study will generate new evidence regarding the acute effects of walnuts in attenuating the adverse effects of HSFM. Furthermore, mitigating the adverse effects of HSFM could yield significant benefits, particularly for patients with insulin resistance, such as the obese and diabetics.

Objective

To evaluate whether acute supplementation with walnuts (*Juglans regia*) attenuates inflammatory markers, oxidative stress, metabolomic profiles, and circulating microRNAs induced by high saturated fat meals (HSFM) in obese and diabetic women.

Methods

The project has been approved by the Ethics Committee of the Faculty of Medicine of Botucatu. The project is currently being registered in Clinical Trials. This study will be randomized and crossover, including women with obesity (body mass index [BMI] ≥ 30) and non-insulin-dependent diabetes aged over 18, recruited during outpatient consultations at the Faculty of Medicine of Botucatu. The exclusion criteria will include: use of dietary supplements, use of corticosteroids in the last 3 months, cancer, heart failure, kidney diseases, liver diseases, lung diseases, neurological diseases, allergy to any component of HSFM or walnuts, and habitual walnut consumption (≤ 3 times per week) in the last month.

The sample size was estimated based on a previous study that showed a 60% reduction in IL-6 levels after meals with HSFM associated with orange juice compared to the control group (without orange juice) [12]. Considering this reduction, a type I error of 5%, and a power of 90%, this study will include 15 individuals.

Patients who sign the Informed Consent Form (ICF) will be evaluated at two time points, separated by a minimum washout of one week. In the first meeting, after fasting for 10 hours, HSFM will be offered with or without 30g of walnuts. In the second meeting, the condition will be switched. This dosage of walnuts refers to the daily recommended intake of nuts proposed by different dietary guidelines [30, 31]. Simple randomization will be performed by a nurse who will not participate in the research. HSFM will be offered in the outpatient clinic of the hospital, and patients will be required to consume

the entire meal and all the walnuts. During the study protocol, patients will be instructed to avoid walnut consumption for 2 weeks before the first study time point.

Blood samples will be collected at time points 0 (immediately before the meal), 15 minutes, 30 minutes, 60 minutes, and 150 minutes after the interventions. From time points 0 to 60 minutes, serum insulin and glucose will be measured, while at time points 0 and 150 minutes, serum biomarkers of inflammation, oxidative stress, circulating microRNAs, and metabolomic profiles will be assessed. Additionally, we will evaluate satiety using a visual analog scale (VAS) at all time points after the meal. Figure 1 illustrates the study design.

[figure not shown]

Figure 1. Randomized crossover study. HSFM, high saturated fat meal.

Biochemical, Inflammation, and Oxidative Stress Analysis

The cytokines TNF-alpha, IL-6, IL-1 β , IL-1ra, IL-8, and IL-10 will be measured using ELISA following the manufacturer's instructions for the kits. Serum concentrations of malondialdehyde (MDA) will be measured by high-performance liquid chromatography (HPLC) based on the reaction with thiobarbituric acid [32]. Insulin will

be measured using a chemiluminescent immunoassay, and glucose will be assessed using the dry chemistry method.

Metabolomic Analysis

Analyses will be conducted using liquid chromatography on a Thermo Dionex Ultimate 3000 system coupled to a high-resolution mass spectrometer, Thermo QExactive Plus, with electrospray ionization operating in both positive and negative modes. Separation will be achieved using a Waters® Acquity BEH C18 column (100 x 2.1 mm x 1.7 μ m particle diameter) maintained at 40 °C with a flow rate of 0.350 mL/min for the mobile phase and a sample injection of 5 μ L. The mobile phases (MP) will be: (MP A) ultrapure water with 0.1% formic acid and 5 mM ammonium formate, and (MP B) methanol with 0.1% formic acid. The chromatographic separation will be performed using a gradient elution mode: 0-1.0 min 5% B; 1.0-3.0 min 35% B; 3.0-13.0 min 95% B; 13.0-17.0 min 95% B; 17.0-20.0 min 5% B. General source conditions will include: sheath gas and auxiliary gas: 50 and 15 arbitrary units, respectively; spray voltage: \pm 3600 V; S-lens voltage: 50 V; capillary temperature: 320 °C; source temperature: 400 °C. Data will be acquired in full ion scan mode over the range of m/z 100-1000 using a resolution of 35,000 FWHM (Full Width at Half Maximum), combined with data-dependent acquisition experiments (DDA) using a resolution of 17,500 FWHM, AGC 1e5, IT 50 ms; NCE 15-35%, and an isolation window of 1.2 Da.

The processing of the raw files obtained from high-resolution liquid chromatography-mass spectrometry (LC-MS) analyses will be conducted using the MS-DIAL software (RIKEN, version 4.9) for the extraction of detected signals, spectral deconvolution, and peak alignment [33]. Parameters for processing will include: MS1 tolerance of 0.005 Da and MS2 tolerance of 0.05 Da; minimum peak height of 1.0E5;

mass width of 0.05 Da; sigma value for deconvolution window of 0.5; and alignment tolerance of 0.3 min and 0.005 Da. A sample blank (extraction solvent) will be used to subtract interfering signals.

For the putative annotation of key metabolites, experimental MS/MS spectra will be compared to data from a spectral library from the laboratory that combined the public library Mass Bank of North America and the commercial NIST MSMS 2020, considering a similarity level of over 80% between spectra. An error of less than 8 ppm for similarity between experimental and theoretical m/z values will also be considered. Detected ions will be exported to Excel (Microsoft Office 2016) for generating a data matrix table. Additionally, molecular formulas will be determined using MS-FINDER (RIKEN, version 3.44) [34]. Analytical standards will be used for compound identification based on comparisons of m/z of precursor ions, fragmentation spectrum, and retention time. Analyses will be performed at the Monash Proteomics & Metabolomics Platform (MPMP).

Circulating MicroRNA Analysis

Following RNA extraction, we will utilize the human miRNA array 4.0 Affymetrix GeneChip® (ThermoFisher Scientific), according to the manufacturer's instructions. This array contains 2,578 sets of probes for mature human miRNAs and 2,025 sets of probes for human pre-miRNAs (stem-loop). Probe sets (a total of 1,996) for determining the presence of human snoRNA and scaRNA are also included in this array. GeneChips will be scanned using the Affymetrix GeneChip G3000 7G scanner with standard settings to capture signal intensities for the miRNAs. Raw intensity data will be imported into the Affymetrix Expression Console software (v1.4.1.46) for signal preprocessing, including background correction using the robust multi-array average

(RMA) algorithm, median polish summarization of probe signals at the probe set level, and quantile normalization across multiple arrays. A detection call for the miRNA signal strength will be performed using the Affymetrix "Detection Above Background" (DABG) algorithm, which generates a p-value for each signal above the background probability. The method will follow the protocol recommended by the manufacturer. Analyses will be conducted at Monash in Hudson Genomics.

Statistical Analysis

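### The walnut-consumption exclusion is written as ≤ 3 times per week, which contradicts the word habitual and, read literally, leaves the most frequent consumers eligible

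*Protocol*

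**What the plan says.** The eligibility rules stand in one paragraph of the protocol's Methods section. The list in question is explicitly one of exclusions: it opens with "The exclusion criteria will include: use of dietary supplements, use of corticosteroids in the last 3 months" and closes with "habitual walnut consumption (≤ 3 times per week) in the last month". The parenthesis is the only definition of habitual intake in the document, and the project summary gives no walnut-intake criterion.

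The same section gives the obesity criterion as "body mass index [BMI] ≥ 30", with the inequality in the expected direction. On walnut intake around the visits, it says "During the study protocol, patients will be instructed to avoid walnut consumption for 2 weeks before the first study time point", and it describes the two visits as "separated by a minimum washout of one week".

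**The concern.** The number contradicts the word it is meant to define. A ceiling of three occasions a week describes occasional intake, so as an exclusion it removes light consumers and admits heavy ones. The evident purpose, limiting background walnut exposure, calls for the opposite.

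The rule decides who is enrolled and whom the results describe. Background intake matters on the protocol's own account: the Introduction states that regular walnut "consumption is associated with better cardiovascular health [23] and insulin response", and the Methods provide that "From time points 0 to 60 minutes, serum insulin and glucose will be measured". With 15 women planned, each one admitted or refused under the wrong rule is 1/15 = 6.7% of the sample.

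**Working it through.** The protocol gives no figure to reproduce here. The check is to apply each reading of the criterion to each possible intake.

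**Inputs.** The criterion and its place in the exclusion list come from the Methods section. Assumption: intake is counted in whole times per week, at most once daily, so k runs from 0 to 7 (8 values).

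**Readings compared.**
- Strict: anyone with k ≤ 3 is excluded.
- Non-consumers spared: as strict, but habitual is taken to mean at least some intake, so k = 0 stays eligible.
- Correction A: k ≥ 3 is excluded.
- Correction B: k > 3 is excluded.

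| k per week | Strict | Non-consumers spared | A (≥ 3) | B (> 3) |
|---|---|---|---|---|
| 0 | excluded | eligible | eligible | eligible |
| 1 | excluded | excluded | eligible | eligible |
| 2 | excluded | excluded | eligible | eligible |
| 3 | excluded | excluded | excluded | eligible |
| 4 to 7 | eligible | eligible | excluded | excluded |

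**Values of k with opposite decisions.**
- Strict against A: k = 0, 1, 2 and 4 to 7, so 3 + 4 = 7 of 8.
- Strict against B: k = 0 to 3 and 4 to 7, so 4 + 4 = 8 of 8.
- Non-consumers spared against A: k = 1, 2 and 4 to 7, so 2 + 4 = 6 of 8.
- Non-consumers spared against B: k = 1 to 3 and 4 to 7, so 3 + 4 = 7 of 8.
- A against B: k = 3 only, so 1 of 8.

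These are counts of frequency values, not shares of women. They show that the written rule is close to a full reversal of either correction, and that the two corrections disagree only at the boundary.

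**Could the sign be a conversion fault?** The ≥ sign for BMI in the same paragraph is in the expected direction, which makes this unlikely. It cannot be excluded from the text alone, because under Metabolomic Analysis the plus-minus sign before 3600 V did not convert properly. That fault, however, is a symbol that failed to render, not a valid sign replaced by its opposite. The sponsor can settle the matter from the source file.

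**The case against.** The strongest reply is that this is a one-character slip with little practical effect. The criterion names habitual consumption, which tells a screener whom to exclude, and the protocol does not show that anyone applied the number literally. That is fair on direction. It does not settle exactly three times a week, so a correction is needed even on the kindest reading.

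A second reply is that the parenthesis may state the tolerated level: up to three times a week is allowed and more is excluded. That gives the same rule as correction B without a reversed sign. The text neither supports nor rules this out, and it too would need rewording and a stated decision at three.

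A third reply is that the design already limits the consequence. Every woman is told to avoid walnuts for two weeks before the first visit, serves as her own control in randomised order, and gives a sample at time 0. The protocol also calls the evidence on walnuts and the inflammatory and antioxidant response inconclusive. This stands: no material bias in the within-woman contrast has been shown. But the avoidance instruction applies to everyone enrolled and does not decide who is eligible.

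It is also fair to say that the strict-reading counts require a woman who eats no walnuts to count as a habitual consumer, which is hard to credit. The counts with non-consumers spared, and the single boundary value, are the more realistic ones.

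**Conclusion.** The concern holds. An operative eligibility threshold is wrong as written and is not corrected elsewhere. Read literally with non-consumers spared, it gives the opposite decision from a corrected rule at 6 or 7 of the 8 frequencies considered, depending on the cut-off. If staff infer the direction, one frequency, exactly three times a week, remains undecided. The counts rest on the assumption of whole frequencies with a maximum of once a day.

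The number of women affected and the size of any effect on outcomes cannot be derived from the protocol. The likely damage is to the definition of the study population and the consistency of screening, more than to the treatment comparison. No sample-size or error-rate figure is affected. It should be fixed, but it does not threaten the main contrast.

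**What to change.** Reword the criterion so that frequent walnut consumers are the excluded group, and state whether a woman at exactly three times a week is excluded. The choice of cut-off is the sponsor's, since the protocol does not settle it. Check the sign against the source file and confirm which rule screening applied; if women were screened under a different reading, record that.

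A minor clarification can go in the same amendment. The avoidance sentence opens as if it covered the whole study but names only the period before the first visit. The one-week washout suggests that avoidance continues between visits without saying so, and one sentence reconciling the two would be enough.

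The cost is a corrected criterion and one added sentence. Sample size, procedures and analysis are unchanged.

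### The walnut-avoidance instruction stops at the first visit and does not cover the washout before the second

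*Protocol*

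**What the plan says.** All of this is in the Methods section of the protocol unless stated otherwise.

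- **Visits.** Women are "evaluated at two time points, separated by a minimum washout of one week". No maximum interval is given and no dietary rule is attached to it. Then: "In the second meeting, the condition will be switched".
- **Avoidance.** The only instruction shown is: "During the study protocol, patients will be instructed to avoid walnut consumption for 2 weeks before the first study time point".
- **Eligibility.** One exclusion criterion is "habitual walnut consumption (≤ 3 times per week) in the last month". It looks back from entry and sets no rule between visits.
- **Allocation.** "Simple randomization will be performed by a nurse who will not participate in the research".
- **Sampling.** "at time points 0 and 150 minutes, serum biomarkers of inflammation, oxidative stress, circulating microRNAs, and metabolomic profiles will be assessed".

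The abstract describes both sessions and adds no restriction on walnuts. The Introduction cites an intervention study in which "acute walnut consumption increased plasma concentrations of polyphenols, as well as enhancing total antioxidant capacity and reducing plasma lipid peroxidation", and notes that acute findings are not consistent across studies.

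**The concern.** The test food is an ordinary food that participants can eat at home. The investigators thought background intake mattered enough to require two clean weeks before visit 1, and the same reasoning applies to visit 2, where the condition is swapped. As worded, the two visits that form each woman's own comparison are prepared differently.

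In a woman who has walnuts first, home walnuts before visit 2 contaminate her control visit. In a woman who has control first, they change the background of her walnut visit. Oxidative stress is an outcome, and it is the area in which the protocol itself cites a short-term walnut effect.

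The eligibility criterion does not clearly close the gap:

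- Taken as printed, with the ≤ sign, it leaves the more frequent eaters eligible.
- If ≥ was meant, it leaves the less frequent eaters eligible.
- If it is meant to remove every habitual eater, only occasional eaters remain and the gap is small.

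**Working it through.** **Timeline from the text.** The protocol applies the term time point to the two visits, so the instruction ends at visit 1. Reading it as a blood draw changes nothing, because the first draw is minute 0 of visit 1.

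| Interval | Length | Avoidance stated |
|---|---|---|
| Before visit 1 | 14 days | 14 days |
| Visit 1 to visit 2 | at least 7 days, no maximum | 0 days |

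**Effect on the estimate.** The protocol has no figure to reproduce here. Inputs: N = 15 and simple randomisation (Methods). Assumed: 1:1 allocation, *k* women affected, and a shift *d* in their 150-minute level at visit 2. SD is that of the within-woman walnut-minus-control difference; the protocol gives no value for it.

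A shift *d* at visit 2 changes walnut minus control by −*d* in a walnut-first woman and by +*d* in a control-first woman.

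*Shift common to all women.* The mean difference moves by *d* × (control-first − walnut-first)/15. For an excess of control-first women (the sign reverses for the opposite excess):

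- 8:7 gives 1/15 = 0.07*d*
- 9:6 gives 3/15 = 0.20*d*
- 10:5 gives 5/15 = 0.33*d*
- 11:4 gives 7/15 = 0.47*d*

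The expectation is zero, but 15 women cannot split evenly. Counting both directions under 1:1 simple randomisation, the probability of 8:7 or 9:6 is 2 × (6435 + 5005)/32768 = 0.70, and of 11:4 is 2 × 1365/32768 = 0.08.

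*Only k women affected.* The largest possible movement, with all of them in one sequence, is (*k*/15)*d*: 0.07*d* for *k* = 1 and 0.20*d* for *k* = 3. The root-mean-square movement is *d*√*k*/15: 0.067*d* for *k* = 1, 0.115*d* for *k* = 3 and 0.258*d* for *k* = 15.

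*Variance.* Over the randomisation, the variance of the mean difference is SD²/15 + *k d*²/225. Dividing by SD²/15 gives the factor 1 + (*k*/15)(*d*/SD)².

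| *d*/SD (assumed) | *k* = 3 | *k* = 15 |
|---|---|---|
| 0.25 | 1.01 | 1.06 |
| 0.5 | 1.05 | 1.25 |
| 1.0 | 1.20 | 2.00 |

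For *k* = 1 at *d*/SD = 0.5 the factor is 1 + (1/15)(0.25) = 1.02.

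**What would reduce it.** A shift equal at 0 and 150 minutes largely cancels in the within-visit change. A period term, if fitted, removes a shift common to all women but not the noise from a few affected women.

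**The case against.** The strongest reply is that this is loose drafting and nobody decided to allow walnuts between visits. The sentence opens by placing the instruction within the study, which would be an odd phrase if avoidance ended when the first meal was served. In a walnut crossover, a washout would also ordinarily mean time free of walnuts. Figure 1 and the participant information are natural places for the rule, and neither is shown. This stands as an account of what was probably intended, and it limits confidence that the rule is absent altogether. It does not mend the sentence, which names its own period, and the washout is stated only as a minimum spacing.

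The second reply is that harm is not shown. The evidence cited in the Introduction concerns acute effects and is mixed. The 10-hour fast, if it also applies at visit 2 (the Methods state it for the first meeting), would put home walnuts at least 10 hours before sampling, and nothing in the protocol shows effects lasting that long. The number of affected women and the shift are assumptions. The larger figures need every woman to eat walnuts between visits, and the 11:4 split is uncommon. All of this stands, and it is why the point ranks low.

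**Conclusion.** The point holds as a minor one. On the text shown, the avoidance period is fixed badly: it controls intake of the test food before one crossover visit and not before the other. The consequence is a possible period effect and added within-woman noise. It is not a systematic dilution of the walnut effect.

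The size cannot be determined from the protocol. It is small unless many participants eat walnuts at home or the shift is large relative to the SD. Confidence is moderate, because the unseen figure or consent text may already extend the rule.

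**What to change.** Replace the instruction with, for example:

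> Patients will be instructed to avoid walnuts, other than the study dose, from 2 weeks before the first visit until the last blood sample of the second visit.

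Ask each woman about walnut intake at both visits and record the answer. If Figure 1 or the consent text already says this, bring the Methods sentence into line with it.

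The cost is one sentence and one question per visit. Participants avoid one food for at least one more week, and for longer if the visits are further apart.

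The direction of the inequality in the habitual-consumption exclusion should be confirmed at the same time, since it determines how many walnut eaters can be enrolled.

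### Glucose and insulin stop at 60 min although blood is drawn at 150 min, so a delayed response could be read as an attenuated one

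*Protocol*

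**What the plan says.** The Methods section fixes five draws per visit: "Blood samples will be collected at time points 0 (immediately before the meal), 15 minutes, 30 minutes, 60 minutes, and 150 minutes after the interventions". It then divides the assays by time. For the glycemic markers, "From time points 0 to 60 minutes, serum insulin and glucose will be measured". The late sample serves the other markers: "while at time points 0 and 150 minutes, serum biomarkers of inflammation, oxidative stress, circulating microRNAs, and metabolomic profiles will be assessed". Glucose and insulin are therefore measured at 0, 15, 30 and 60 min and not at 150 min. No reason is given for stopping at 60 min, and no other late measurement of either analyte is planned.

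The project summary before the Introduction states the aim as to "evaluate whether acute walnut supplementation attenuates the inflammatory response, oxidative stress, glycemic response", among other responses. The two conditions differ only in the walnuts: "HSFM will be offered with or without 30g of walnuts".

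For the better insulin response seen with regular walnut consumption, the Introduction offers a tentative mechanism: "possibly due to the regulation of insulin response by reducing the activity of carbohydrate-digesting enzymes".

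The Statistical Analysis section plans GEE for repeated measures. It names no glycemic summary such as an area, a peak or a time to peak.

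**The concern.** Lower activity of carbohydrate-digesting enzymes may slow the rise in glucose and insulin. A slower rise can move the excursion later without making it smaller. If much of the excursion lies beyond 60 min, a lower early curve with walnuts has two explanations, less response or later response, and measurements that end at 60 min may not tell them apart. Any such error would point towards the study hypothesis.

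This is a matter of what is measured. A statistical analysis plan can choose a model or a summary, but it cannot recover a value that was never assayed. Here the blood is already in hand.

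**Working it through.** The protocol gives no glycemic figure to reproduce. Its only sample-size figure, 15 women, rests on IL-6 and does not bear on this point. The check asks how a pure delay would look on the planned sampling times.

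**Inputs from the protocol (Methods).** Assay times for glucose and insulin: 0, 15, 30, 60 min. Further draw: 150 min. 15 women, two visits each.

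**Assumptions, not in the protocol.** Increment above baseline g(t) = [(t/tp) × exp(1 - t/tp)]^k, with peak height 1, peak time tp = 30, 45, 60, 75 or 90 min, and shape k = 1, 2 or 3. That makes 15 curves. Walnuts only shift the curve 15 min later, g(t - 15), so the total area is unchanged. Areas use the trapezoid rule on the sampled times.

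**One case in full (tp = 60, k = 2).**

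| min | 0 | 15 | 30 | 60 | 150 |
|---|---|---|---|---|---|
| without walnuts | 0 | 0.280 | 0.680 | 1.000 | 0.311 |
| delayed 15 min | 0 | 0 | 0.280 | 0.927 | 0.416 |

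- 0-60 min area, without walnuts: 7.5 × 0.280 + 7.5 × (0.280 + 0.680) + 15 × (0.680 + 1.000) = 34.5.
- 0-60 min area, delayed: 0 + 7.5 × 0.280 + 15 × (0.280 + 0.927) = 20.2. Change: 20.2/34.5 - 1 = -41%.
- Adding 60-150 min: 34.5 + 45 × (1.000 + 0.311) = 93.5, and 20.2 + 45 × (0.927 + 0.416) = 80.6. Change: -14%.

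In this case the delayed curve is lower at 15, 30 and 60 min, as a true attenuation would be. Only the 150-min value (0.416 against 0.311) points to a delay.

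**All 15 curves (range over k).**

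| Peak (min) | Change in 0-60 area | Change in 0-150 area | Delayed curve at 60 min | Delayed curve at 150 min |
|---|---|---|---|---|
| 30 | -30% to -35% | -5% to +6% | higher | higher |
| 45 | -34% to -40% | -9% to -10% | higher | higher |
| 60 | -36% to -44% | -12% to -17% | lower | higher |
| 75 | -38% to -47% | -13% to -18% | lower | higher |
| 90 | -39% to -49% | -14% to -18% | lower | higher |

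The table shows three things.

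1. With peaks at 30 or 45 min (6 of 15 curves), the delayed curve crosses above the other at 60 min, so the planned data would hint at a delay. With peaks at 60 to 90 min (9 of 15), it is lower at every planned post-meal time.
2. The 150-min value is higher under delay in all 15 curves. The contrast is small when the peak is early: at tp = 30, k = 2 it is 0.018 against 0.008.
3. The 0-150 min area does not settle the matter. It still shows a pure delay as a reduction of up to 18%, because one 90-min trapezoid replaces the unsampled part of the curve.

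**Not only an area effect.** The mean of the 15, 30 and 60-min increments falls by 32% to 46% over the same curves, so a GEE averaging over those times would show the same pattern.

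**Other delays.** With k = 2 and peaks at 45 to 75 min, delays of 10 to 30 min lower the 0-60 min area by 25% to 73%, and the 0-150 min area by 6% to 31%.

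**The case against.** The strongest reply is that the problem is conditional throughout. The Introduction offers the mechanism only as a possibility, and for regular rather than single consumption. It speaks of lower enzyme activity; that this delays the response without reducing it is an inference. A lower early rise may be a real attenuation. The curve family, peak times and lag are all assumed, and a 15-min lag forces the 15-min increment to zero, which enlarges the contrast. The protocol does not give the meal's carbohydrate content, so the peak time cannot be judged from it. An early-phase window is also a legitimate endpoint if it is described as one. All of this stands, and it limits the percentages to illustration.

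Two stronger readings are tempting. A reader might infer that the 0-60 min data would show a false benefit and that the conclusion would be biased in favour of walnuts. The documents do not support this: the error needs both a material delay and a peak at about 60 min or later, and neither is established. A reader might also infer that the planned times can never separate a later response from a smaller one. With a peak at 30 or 45 min and a 15-min delay, they partly can.

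It is also fair to object that the 150-min sample is no cure. If slower digestion is modelled as a 25% stretch of the curve with equal total area (peak 60 min), the 0-60 min area falls by 27% to 36% and the 0-150 min area still falls by 17% to 19%. That rules out the 0-150 min area as the test of attenuation. It leaves the case for looking at the 150-min value itself.

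**Conclusion.** The point holds in a conditional form. The protocol limits glucose and insulin to the first 60 min, lists the glycemic response among its aims in the summary, and draws a later sample that it does not use for these analytes. If walnuts delay the response and the peak is at about 60 min or later, a delay could be reported as attenuation.

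The 30% to 49% fall in the 0-60 min area shows how large such an artefact can look under the assumed curves and a pure 15-min delay. It is not an estimate of bias in this trial.

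The weight is modest. The Objective section omits the glycemic response and the sample size rests on IL-6, so this is a secondary aim and the IL-6 basis of the trial is untouched. It is best treated as a cheap improvement.

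**What to change.** In Methods, change the sentence on assay times so that glucose and insulin are also measured in the 150-min sample. In the analysis:

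- Include 150 min as a time point in the GEE, with a condition-by-time term, and report the walnut contrast at 150 min.
- Read lower early values with walnuts together with a higher 150-min value as suggesting a delay, not attenuation.
- Do not rest a claim of attenuation on the 0-150 min area alone.
- Word any 0-60 min finding as an early-phase response.

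The cost is 15 women × 2 visits × 2 analytes = 60 extra routine assays, on top of 15 × 2 × 2 × 4 times = 240 already planned. No extra draw or visit time is needed. Because nothing is sampled between 60 and 150 min, some ambiguity will remain and the report should say so.
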